### 6.2.5 Specimen submission using the Alliance Biospecimen Management System

USE OF THE ALLIANCE BIOSPECIMEN MANAGEMENT SYSTEM (BioMS) IS MANDATORY AND ALL SPECIMENS MUST BE LOGGED AND SHIPPED VIA THIS SYSTEM.

BioMS is a web-based system for logging and tracking all biospecimens collected on Alliance trials. Authorized individuals may access BioMS at the following URL: [REDACTED] using most standard web browsers (Safari, Firefox, Internet Explorer). For information on using the BioMS system, please refer to the ‘Help’ links on the BioMS webpage to access the on-line user manual, FAQs, and training videos. To report technical problems, such as login issues or application errors, please contact: [REDACTED] For assistance in using the application or questions or problems related to specific specimen logging, please contact: [REDACTED]

## 6.3 MR/CT data submission requirements

### 6.3.1 Overview

For all patients enrolled, images will be acquired per [Appendix II](#) and transmitted electronically from each participating site to the Imaging and Radiation Oncology Core QA center at The Ohio State University (IROC Ohio).

Images and local interpretation reports will be collected digitally and submitted for centralized, retrospective re-review. Images will be collected locally and submitted within 14 days of image acquisition.

Images must be submitted for all MRI/CTs required at timepoints outlined in [Section 5.0](#) (baseline, during treatment, survival and clinical follow up, confirmation of response and progression, or for patients on Cohort B, any scans related to clinical care or follow-up post-surgery or radiation).

### 6.3.2 Imaging submission instructions

Complete data sets in digital DICOM format should be submitted to IROC Ohio within 14 days of image acquisition.

BMP files, JPG files, or hard copies (films) are not acceptable. The raw data of the entire study should be saved until the scan is accepted by IROC. De-identify the patient data using institutional procedures to remove patient name and medical record number while preserving the Alliance patient ID number and protocol number. The de-identified digital images may be temporarily burned to a CD or transferred to a PC based system.

Data should be transferred electronically (recommended) to IROC as follows:

- 1) TRIAD based data transfer (see [Section 6.3.3](#))

The standard TRIAD based data transfer approach will be provided separately through IROC efforts per the request by participating sites before their first data submission.

2) Web Transfer [REDACTED]

Any PCs with internet access and web browser (e.g., Internet Explorer, Mozilla Firefox) can be used to web transfer DICOM images and other required files to IROC. The standard Web Transfer information will be provided separately through the specific trial e-mail, per the request by participating sites before their first data submission.

3) FTP Transfer

Any FTP software can be used to initiate access to the secure FTP Server of IROC. The standard FTP access information will be provided separately through the specific trial e-mail, per the request by participating sites before their first data submission.

4) Mail/CD Shipment

Only if electronic data transfer approaches cannot be achieved, the de-identified images in digital DICOM format can be burned to a CD and mailed to IROC Ohio. Submit only one patient's images per CD, with the patient's Alliance ID number, study type, date of scans, and name of submitting institution.

Submit these data to:

Once the imaging data submission is done, send an e-mail to IROC Ohio at the specific trial email [REDACTED] to inform that the study has been submitted from the institution. Please include the basic information of submitted data sets as follows:

- 1) Alliance patient ID number
- 2) Scan time point (i.e., baseline)
- 3) Date of scans
- 4) Institution name

IROC will acknowledge receipt of the imaging data via email confirmation to the institution within 1 business day of receipt, and will notify the institution and Alliance imaging committee of the quality check report within 3 business days.

### 6.3.3 Using TRIAD image submission

Transfer of Images and Data (TRIAD) is the American College of Radiology's (ACR) image exchange application. TRIAD provides sites participating in clinical trials a secure method to transmit images. TRIAD anonymizes and validates the images as they are transferred.

TRIAD Access Requirements:

- A valid CTEP-IAM account and linked ID.me account (ID.me accounts are required for all newly created CTEP-IAM accounts and by July 1, 2023 for all users);

- Registration type of: Associate (A), Associate Plus (AP), Non-Physician Investigator (NPIVR), or Investigator (IVR). Refer to the CTEP Registration Procedures section for instructions on how to request a CTEP-IAM account and complete registration in RCR; and
- TRIAD Site User role on an NCTN, ETCTN, or other relevant roster.

All individuals on the Imaging and Radiation Oncology Core provider roster have access to TRIAD and may submit images for credentialing purposes, or for enrollments to which the provider is linked in OPEN.

#### TRIAD Installation:

To submit images, the individual holding the TRIAD Site User role will need to install the TRIAD application on their workstation. TRIAD installation documentation is available at [REDACTED]

This process can be done in parallel to obtaining your CTEP-IAM account and RCR registration.

For questions, contact TRIAD Technical Support staff via email [REDACTED]

## 7.0 TREATMENT PLAN/INTERVENTION

Protocol treatment is to begin  $\leq 10$  days of registration. **EKG, Echo (or MUGA), O2 Saturation, and skin exam must be performed prior to initiation of treatment for safety as required in Section 5.0. See Dose Modifications in Section 8.2 prior to initiating treatment.** For questions regarding treatment, please see the study contacts page.

**Prior to initiating treatment, physicians must discuss caffeine limitation while on this study with the patient. See Section 8.1.11 for more information.**

It is acceptable for individual chemotherapy doses to be delivered  $\leq$  a 24-hour (business day) window before and after the protocol-defined date for Day 1 of a new cycle. For example, if the treatment due date is a Friday, the window for treatment includes the preceding Thursday through the following Monday. In addition, patients are permitted to have a new cycle of chemotherapy delayed up to 7 days for major life events (e.g., serious illness in a family member, major holiday, vacation that cannot be rescheduled) without this being considered a protocol violation. Documentation to justify this delay should be provided.

### 7.1 Vemurafenib + cobimetinib

Each cycle will consist of 28 days.

Agent	Dose	Route	Administration Days	Frequency
Vemurafenib	960 mg	P.O.	Days 1-28	Twice daily for 28 days
Cobimetinib	60 mg	P.O.	Days 1-21	once daily for 21 days, followed by 7 days off

For both arms, a cycle will be 28 days. Patients will be treated with vemurafenib 960mg po twice daily for 28 days, and cobimetinib 60mg po once daily for 21 days, followed by 7 days off. Dose modifications will be instituted for toxicity as per [Section 8.0](#). Contrast- MRI (or CT, see [Section 5.0](#)) will be performed every 8 weeks as outlined in [Section 5.0](#). See [Section 11.0](#) for response criteria.

If a dose of vemurafenib is missed, it can be taken up to 4 hours prior to the next scheduled dose. If a dose of cobimetinib is missed (i.e. 6 hours or more late), do not make up that dose; resume dosing with the next scheduled dose.

If cobimetinib meets criteria to be discontinued due to protocol dose modifications and vemurafenib does not, cobimetinib may be discontinued and patient may continue on single agent vemurafenib therapy.

If vemurafenib meets criteria to be discontinued due to protocol dose modifications and cobimetinib does not, vemurafenib may be discontinued and patient may continue on single agent cobimetinib therapy.

See complete dose modifications in [Section 8.0](#).

#### 7.1.1 Cohort A

For Cohort A, patients should receive treatment for up to 4 cycles with vemurafenib + cobimetinib (unless progression, unacceptable toxicity, or patient withdrawal from study occurs). See [Section 12.0](#) for additional information. After 4 cycles of vemurafenib and cobimetinib, surgery or radiation for definitive therapy should be performed. Continuation of vemurafenib and cobimetinib beyond 4 cycles in cohort A will require approval from the radiation oncology chair and study chair. If patient stays on study for longer than 4 cycles, visits and labs at the beginning of every cycle are still required with scans every 2 cycles, as per the study calendar.

- **For patients that achieve CR**, they will undergo definitive radiation.
- **For patients with any response that is not CR or better**, the decision of therapy between surgery, or radiation, or both, is at the discretion of the treating physician.

**For patients who go on to receive radiation**, the pre-treatment scan would be used as a guide for radiation planning. See [Section 7.2](#) for radiation guidelines. Vemurafenib and cobimetinib need to be stopped at least two weeks prior to initiation of radiation therapy. For purposes of radiation planning, if duration of BRAF/MEK inhibitor treatment needs to be extended this will be allowed, for a maximum length of 4 additional weeks (i.e., 5 cycles maximum).

**In special cases**, if radiation or surgery are not recommended for the patient because of potential risks, then the patient may continue on cobimetinib and vemurafenib past 4 cycles, until disease progression or unacceptable adverse events. **However, continuation of treatment can only be granted with approval from the radiation oncologist and study chair.** A request, with accompanying rationale, must be sent to the radiation oncologist and protocol coordinator. Approval must be obtained via email prior to Cycle 5 drug shipment. The email containing the approval must also be submitted via Rave as supporting documentation.

### 7.1.2 Cohort B

For Cohort B, patients will receive 4 cycles of study drug therapy (unless progression, unacceptable toxicity, or patient withdrawal from treatment occurs). After 4 cycles of vemurafenib + cobimetinib, the patient may go on to receive treatment per the discretion of the treating physician, including radiation, surgery or continued treatment with vemurafenib + cobimetinib. Treatment with vemurafenib + cobimetinib can be continued until CR, PR, or SD but must be discontinued with PD. The BRAF and MEK inhibitors need to be stopped at least two weeks before initiation of radiation therapy.

## 7.2 Radiotherapy guidelines for Cohort A

### 7.2.1 Definition of target volumes

The pre-surgical and most recent pre-irradiation scans performed no greater than one month prior to the CT simulation scan should be used to guide radiation planning. Target volume should include any radiographically visible residual disease and surfaces to which the tumor was previously adherent to that may be at risk for harboring residual microscopic disease.

- GTV = Gross target volume, interpreted as any residual tumor (residual enhancing nodules and cysts)
- CTV = Clinical target volume, should encompass the GTV plus surgical bed/any areas of microscopic residual (surfaces of pre-op tumor contact) adjusting for post-operative anatomic shifts. Often 0-5 mm nonuniform expansion may be added per clinician discretion to capture additional microscopic disease although typically expansion into brain parenchyma is not needed.
- PTV = Planning target volume, as standard for immobilization choice and institutional practice, typically range of 3-5 mm should be employed. Daily image-guided radiation therapy (IGRT) is recommended.
- Because 15% of cystic tumors can enlarge during RT, weekly verification CT or MR is recommended.

### 7.2.2 Dose prescription

The recommended radiation therapy regimen is 54 Gy at 1.8 Gy per fraction delivered daily, Monday

through Friday, utilizing image guidance (IGRT). If able to safely meet normal tissue constraints:

- GTV  
 $\geq 99\%$  of the GTV should receive 54 Gy  
 $D_{\max}$  GTV <59 Gy
- CTV  
 $\geq 99\%$  of the CTV should receive  $\geq 95\%$  prescription dose  
 $D_{\max}$  CTV <59 Gy
- PTV  
 $\geq 95\%$  of the PTV should receive  $\geq 95\%$  prescription dose  
 $D_{\max}$  PTV <59 Gy

### 7.2.3 Normal tissue constraints

Normal Structure Constraints

Name of Structure	Dosimetric parameter	
SpinalCord	$D_{\max}$	$\leq 50$ Gy
BrainStem	$D_{\max}$	$\leq 55$ Gy
OpticChiasm	$D_{\max}$	$\leq 55$ Gy
OptNrv_L_ and OptNrv_R_	$D_{\max}$	$\leq 55$ Gy
Retina_L_ or Retina_R_	$D_{\max}$	$\leq 45$ Gy
Brain	$D_{5\%}$	$\leq 57$ Gy
Lens_L_ or Lens_R_	$D_{\max}$	$\leq 7$ Gy

$D_{\max}$  defined for a volume less than or equal to 0.03cc.

## 8.0 DOSE AND TREATMENT MODIFICATIONS

### 8.1 Ancillary therapy, concomitant medications, and supportive care

**8.1.1 Patients should not receive any other agent** which would be considered treatment for the primary neoplasm or impact the primary endpoint.

**8.1.2 Patients should receive full supportive care while on this study.** This includes blood product support, antibiotic treatment, and treatment of other newly diagnosed or concurrent medical conditions. All blood products and concomitant medications such as antidiarrheals, analgesics, and/or antiemetics received from the first day of study treatment administration until 30 days after the final dose will be recorded in the medical records.

**8.1.3 Treatment with other chemotherapeutic agents may not be administered** except for steroids given for adrenal failure or pituitary hormone replacement therapy; hormones administered for non-disease-related conditions (e.g., insulin for diabetes); and intermittent use of dexamethasone as an antiemetic.

**8.1.4 Antiemetics** may be used at the discretion of the attending physician.

**8.1.5 Diarrhea management is per the discretion of the treating physician.** Diarrhea could be managed conservatively with medications such as loperamide. Patients with severe diarrhea should be assessed for intravenous hydration and correction of electrolyte imbalances.

**8.1.6 Palliative radiation therapy may not be administered** except for radiation therapy given for patients on Cohort B as outlined in [Section 7.2](#).

#### **8.1.7 Alliance policy concerning the use of growth factors**

Blood products and growth factors should be utilized as clinically warranted and following institutional policies and recommendations. The use of growth factors should follow published guidelines of the American Society of Clinical Oncology Clinical Practice Guideline Update. J Clin Oncol 33: 3199-3212, 2015 and American Society of Clinical Oncology – American Society of Hematology Clinical Practice Guideline Update on the Use of Epoetin and Darbepoetin in Adult Patients with Cancer. J Clin Oncol 28:4996-5010, 2010.

Epoetin (EPO): Use of epoetin in this protocol is permitted at the discretion of the treating physician.

#### **8.1.8 Hypersensitivity reactions**

Treat hypersensitivity reactions to vemurafenib and cobimetinib as per institutional standards.

#### **8.1.9 CYP3A4 inhibitors**

Chronic concomitant treatment with strong inhibitors of CYP3A4 is not allowed during on this trial. The following drugs are EXAMPLES of strong inhibitors of CYP3A4 and are not allowed during treatment with vemurafenib and cobimetinib.

- Indinavir
- Clarithromycin
- Ketoconazole

Because lists of these agents are constantly changing, please consult and review any drugs for their potential to inhibit CYP3A4. Examples of resources that may be utilized include the product information for the individual concomitant drug in question, medical reference texts such as the Physicians' Desk Reference, the FDA website, or your local institution's pharmacist.

If concurrent short term ( $\leq$  14 days) use of a moderate CYP3A4 inhibitor is unavoidable, reduce the cobimetinib dose to 20 mg. After discontinuation of the moderate CYP3A4 inhibitor, resume cobimetinib at the previous dose.

Investigators may provide patients with the wallet handout card provided [Appendix V](#).

#### 8.1.10 CYP3A4 inducers

Chronic concomitant treatment with strong inducers of CYP3A4 is not allowed during on this trial. The following drugs are EXAMPLES of strong inducers of CYP3A4 and are not allowed during treatment with vemurafenib and cobimetinib.

- Rifampin
- Carbamazepine

Because lists of these agents are constantly changing, please consult and review any drugs for their potential to induce CYP3A4. Examples of resources that may be utilized include the product information for the individual concomitant drug in question, medical reference texts such as the Physicians' Desk Reference, the FDA website, or your local institution's pharmacist.

Investigators may provide patients with the wallet handout card provided [Appendix V](#).

#### 8.1.11 CYP1A2 substrates

Chronic concomitant treatment with substrate of CYP1A2 with a narrow therapeutic index or sensitive substrate is not allowed on this trial. The following drugs are EXAMPLES of substrates of CYP1A2 with a narrow therapeutic index or sensitive substrate and are not allowed during treatment with vemurafenib:

- Caffeine: Limit to 200 mg/day. It is important that you discuss this limit with your patient prior to initiating treatment. We recommend that you discuss the patient's typical daily food and beverage intake to determine their average caffeine consumption, as well as to discuss strategies and best practices for limiting caffeine to 200 mg/day.
- Tizanidine
- Duloxetine
- Melatonin

Because lists of these agents are constantly changing, please consult and review any drugs for their potential to be CYP1A2 substrate. Examples of resources that may be utilized include the product information for the individual concomitant drug in question, medical reference texts such as the Physicians' Desk Reference, the FDA website, or your local institution's pharmacist.

Investigators may provide patients with the wallet handout card provided [Appendix V](#).

#### 8.1.12 QT prolongation: Chronic concomitant treatment with drugs that are known to prolong the QT interval/are associated with Torsades should be avoided, as vemurafenib can cause QT prolongation and arrhythmia. See [REDACTED] (registration required but is free).

- 8.1.13 Radiation recall:** Vemurafenib has been reported to cause radiation recall. For patients who develop CNS toxicity and were previously irradiated for craniopharyngioma, consider performing MRI brain to evaluate.
- 8.1.14 Malignancy:** Both vemurafenib and cobimetinib are associated with skin malignancies. Patients should report any new or suspicious skin lesions promptly, and have skin exams per [Section 5.0](#). In addition, vemurafenib is associated with RAS-related malignancies, and any suspicious symptoms should undergo prompt workup. In addition, vemurafenib is associated with the formation of colon polyps, and patients should follow national guidelines for colon screening.
- 8.1.15 Rash:** Both agents are associated with rash and cobimetinib is associated with photosensitivity. Patients should avoid sun exposure and practice good skin care. Consider dermatology consult as needed in the setting of rash.
- 8.1.16 Ocular toxicity:** Vemurafenib is known to cause uveitis, and cobimetinib is known to cause retinopathy. In addition, due to the location of the tumor, patients with craniopharyngioma are known to have visual field defects. Regular eye exams should be performed as per [Section 5.0](#), and patients should report any visual changes promptly. Consider treatment with steroids for uveitis. Serous retinopathy may be treated with topical corticosteroid eye drops.
- 8.1.17 Bleeding:** Cobimetinib leads to an increased bleeding risk. Hemorrhage, including major hemorrhages, defined as symptomatic bleeding in a critical area or organ, can occur with cobimetinib. In clinical studies with cobimetinib, events of cerebral hemorrhage, GI tract hemorrhage, reproductive tract hemorrhage, and hematuria have been reported. Patients on anticoagulation should undergo increased frequency of monitoring while on treatment.
- 8.1.18 Pneumonitis:** Cobimetinib has been associated with pneumonitis. In the setting of suspected pneumonitis, consider CT scan, PFTs, pulmonary consult, and bronchoscopy, and consider treatment with steroids or referral to pulmonary and infectious disease specialists.

## 8.2 Dose modifications

- If multiple adverse events are seen, administer dose based on greatest modification required for any single adverse event observed.
- Modifications apply to treatment given in the preceding cycle and are based on adverse events observed since the prior dose.
- If study agent is held for >28 days, study agent will be discontinued.
- Dose modifications can be communicated to patients taking oral agents at home at any point in the cycle (i.e. if there is Grade III diarrhea at home).
- If cobimetinib meets criteria to be discontinued due to protocol dose modifications and vemurafenib does not, cobimetinib may be discontinued and patient may continue on single agent vemurafenib therapy.
- If vemurafenib meets criteria to be discontinued due to protocol dose modifications and cobimetinib does not, vemurafenib may be discontinued and patient may continue on single agent cobimetinib therapy.
- Descriptors below utilize CTCAE version 4.0. See Sections [9.1](#), [9.2](#) and [9.3](#) for routine AE reporting requirements. Expedited reporting via CTEP-AERS may be required for some adverse events (See [Section 9.3](#)). CTCAE version 5.0 must be used for serious adverse event reporting through CTEP-AERS.
- Please see IB for vemurafenib and cobimetinib or contact study chair for additional guidance.

**8.2.1 Dose levels**

Dose Level	Drug Name	Dose
0*	Vemurafenib	960 mg twice/day
-1	Vemurafenib	720 mg twice/day
-2	Vemurafenib	480 mg twice/day

\*Dose level 0 refers to the starting dose.

Dose Level	Drug Name	Dose
0*	Cobimetinib	60 mg once/day
-1	Cobimetinib	40 mg once/day
-2	Cobimetinib	20 mg once/day

**8.2.2 Dose modifications for vemurafenib and cobimetinib:****8.2.2.1 Gastrointestinal toxicity**

- For **grade 2 or 3 diarrhea**, delay cobimetinib and vemurafenib until grade  $\leq 1$ , then resume vemurafenib at same dose and cobimetinib at 1 dose level decreased.
- For **grade 4 diarrhea**, discontinue cobimetinib and vemurafenib.
- For **grade 3 or 4 nausea or grade 3 vomiting**, delay cobimetinib and vemurafenib until grade  $\leq 2$ , then resume vemurafenib at same dose and cobimetinib at 1 dose level decreased.
- For **grade 4 vomiting**, discontinue cobimetinib and vemurafenib.

**8.2.2.2 Hepatic toxicity**

- For **grade 3 transaminase increased and/or blood bilirubin increased**, delay cobimetinib and vemurafenib until grade  $\leq 1$ , then resume cobimetinib at same dose and vemurafenib at 1 dose level decreased
- For **grade 4 transaminase increased and/or blood bilirubin increased**, discontinue vemurafenib and cobimetinib.

**8.2.2.3 Renal toxicity**

- For **grade 3 acute kidney injury or hematuria**, delay vemurafenib until

grade  $\leq 1$ , then resume at 1 dose level decreased.

- For **grade 4 acute kidney injury, hematuria, or grade 4 creatinine increase**, discontinue vemurafenib and cobimetinib.

#### 8.2.2.4 Skin toxicity

- For **grade 3 maculopapular rash and/or grade 3 pruritus**, delay vemurafenib until grade  $\leq 1$ , then resume at 1 dose level decreased.
- For **grade 4 maculopapular rash**, discontinue vemurafenib and cobimetinib.
- For **grade 3 acneiform rash**, delay cobimetinib until grade  $\leq 1$ , then resume at 1 dose level decreased.
- For **grade 4 acneiform rash**, discontinue cobimetinib.
- For **grade 3 pruritus or photosensitivity**, delay cobimetinib and vemurafenib until grade  $\leq 1$ , then resume at cobimetinib at same dose and vemurafenib at 1 dose level decreased.
- For **grade 4 pruritus or photosensitivity**, discontinue cobimetinib and vemurafenib.
- For **Stevens Johnson syndrome**, discontinue vemurafenib and cobimetinib.

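### Grade 3 pruritus falls under two skin-toxicity rules in Section 8.2.2.4, and only one of them holds cobimetinib

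*Combined protocol and SAP*

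**What the plan says.** Section 8.2.2.4 has seven bullets, and two of them cover grade 3 pruritus.

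- **Bullet 1** is triggered by "grade 3 maculopapular rash and/or grade 3 pruritus". Vemurafenib is held until grade 1 or lower and restarted one level down. Cobimetinib is not mentioned.
- **Bullet 5** is triggered by "grade 3 pruritus or photosensitivity". Both drugs are held until grade 1 or lower. Cobimetinib then restarts at its previous dose and vemurafenib one level down.

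The grade 4 rules do not overlap. One covers "grade 4 maculopapular rash" and another covers "grade 4 pruritus or photosensitivity".

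Two general provisions in Section 8.2 bear on the point: "If multiple adverse events are seen, administer dose based on greatest modification required for any single adverse event observed" and "Please see IB for vemurafenib and cobimetinib or contact study chair for additional guidance".

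**The concern.** The first trigger is joined by and/or, so pruritus without rash meets it. The same isolated pruritus also meets the fifth. The section does not say which one governs.

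A site that stops reading at bullet 1 has a complete instruction and no reason to look further. It may keep cobimetinib going through an event for which bullet 5 requires a hold. Another site, following bullet 5, would interrupt it. What is at stake is consistent and safe handling of a grade 3 toxicity across sites, not the response-rate analysis.

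**Working it through.** The protocol states no figure on this point, so there is none to reproduce. The check is a comparison of text, followed by a rough sizing.

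**1. The two rules side by side, for isolated grade 3 pruritus**

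| | Bullet 1 | Bullet 5 |
|---|---|---|
| Vemurafenib | hold to grade ≤1, then one level lower | hold to grade ≤1, then one level lower |
| Cobimetinib | not mentioned | hold to grade ≤1, then same dose |

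The only difference is the cobimetinib interruption.

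**2. Does silence mean continue?** Section 8.2.2 generally names each drug it wants held. For "grade 3 transaminase increased and/or blood bilirubin increased" (8.2.2.2) it names both. For "grade 3 acute kidney injury or hematuria" (8.2.2.3) it names vemurafenib alone. For grade 3 acneiform rash (8.2.2.4) it names cobimetinib alone. Against that pattern, bullet 1 can reasonably be read as leaving cobimetinib running.

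**3. Does another provision settle it?** The greatest-modification rule is conditioned on multiple adverse events. Isolated pruritus is one event under two rules, so the rule helps only by analogy. The catch-all in 8.2.2.15 covers toxicities not listed elsewhere, so it does not apply.

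**4. Where does pruritus belong?** At grade 4, maculopapular rash stands alone and pruritus is paired with photosensitivity. Bullet 5 has that same pairing at grade 3; bullet 1 departs from it. The risk lists in 9.5.1 and 9.5.2 name pruritus for both drugs, which fits a rule that holds both.

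**5. How many patients?** Section 1.6.3 lists the grade ≥3 events seen in at least 5% of the 63 BRAF-inhibitor-naive patients in the phase Ib combination study. Pruritus is not among them. Since 3/63 = 4.8% and 4/63 = 6.3%, a complete list implies at most 3 of 63. The maximum accrual is 36 (13.3.1). Expected patients = 36 × x/63:

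| x of 63 | Rate | Expected of 36 | Exact 95% upper limit for the rate | Upper limit × 36 |
|---|---|---|---|---|
| 0 | 0% | 0 | 5.7% | 2.0 |
| 1 | 1.6% | 0.57 | 8.5% | 3.1 |
| 2 | 3.2% | 1.14 | 11.0% | 4.0 |
| 3 | 4.8% | 1.71 | 13.3% | 4.8 |

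The upper limits are two-sided Clopper-Pearson limits. The phase III study's list of higher-grade events, which goes down to 2.4% of 254 combination patients, does not name pruritus either. It covers only events more frequent with the combination, so it suggests a lower rate without bounding it.

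**6. How many doses per event?** Cobimetinib is given on 21 of every 28 days, so four cycles schedule 4 × 21 = 84 doses. If the cycle calendar is not reset, a hold of d consecutive days (7 ≤ d ≤ 28) covers between d − 7 and min(d, 21) scheduled doses:

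- d = 7: 0 to 7
- d = 14: 7 to 14
- d = 21: 14 to 21
- d = 28: 21

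The largest difference is 21/84 = 25% of the four-cycle schedule. The cobimetinib dose level is the same afterwards under either bullet.

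**The case against.** The strongest reply is that this is overlap rather than contradiction. Bullet 1 never tells a site to continue cobimetinib, and holding both drugs complies with every word of both bullets. The principle of the greatest-modification rule points only toward bullet 5, and a site in doubt can consult the investigator's brochure or the study chair. This is fair, and it limits the risk. It does not remove it: the drafting pattern makes the narrower reading natural, and a site asks for guidance only if it notices both bullets.

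The sizing is also open to challenge, and these points stand as qualifications:

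- The count of 1.7 is an expectation, not a ceiling; sampling error takes it to about 4.8.
- The 63 patients come from a study that used several doses and schedules (Section 1.5), so the rate may not transfer.
- Section 5.0 dates a new cycle from the day drug is actually started, so a hold that crosses a cycle boundary may postpone doses rather than lose them.
- Cohort B patients may continue past four cycles, so 84 doses need not be their full course.

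Finally, one could argue that the repair might go the other way, by taking pruritus out of bullet 5. The protocol does not state its intent. But that repair would delete an express safety hold and break the match with the grade 4 rules, so the two repairs are not equally well supported.

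**Conclusion.** The concern holds, as a minor one. The duplicate listing is certain. That the two bullets lead to different cobimetinib handling rests on reading bullet 1's silence as continuation, which the drafting of Section 8.2.2 supports. No provision expressly resolves it.

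Few patients are likely to be affected, and the numbers are conditional: they assume that the Section 1.6.3 list is complete, that its rate applies here, and that the cycle calendar is not reset. They count patients with the event, not patients handled wrongly, and they are not adjusted for exposure, although Cohort A normally stops at four cycles. The finding does not depend on them.

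Nor does it depend on what follows a hold of more than 28 days. On that, Sections 7.1 and 8.2 allow one drug to continue alone, while the Schema and Section 12.1 can be read as stopping both.

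**What to change.** In the first bullet of Section 8.2.2.4, delete the last four words of the trigger "grade 3 maculopapular rash and/or grade 3 pruritus", so that it covers maculopapular rash only. Bullet 5 then governs grade 3 pruritus alone, in line with the grade 4 rules, and the vemurafenib instruction does not change. A patient with both grade 3 rash and grade 3 pruritus then has two adverse events, to which the greatest-modification rule applies as written.

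The change costs one edit of four words. Its clinical price is a cobimetinib pause, without dose reduction, in the few affected patients; bullet 5 already requires that pause.
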